3.3. Study Treatment

The trial interventions will consist of a single subcutaneous (sc) immunization of PROSTVAC V or placebo in Week 1, followed by six PROSTVAC F or placebo immunizations administered in Weeks 3, 5, 9, 13, 17, and 21. Each immunization will be accompanied by administration of sc GM-CSF or placebo on the day of immunization and for the subsequent three days (sc injection within 5 mm of the original PROSTVAC VF or placebo injection site). The Treatment phase of this trial lasts for five months and is followed by an End-of-Treatment (Week 25)/Early Termination visit. During the Treatment phase, subjects will continue to be treated with vaccination therapy through PSA and/or radiological progression.

3.4. Dose Adjustment

See the Dose Reductions section of the protocol.

4. General Statistical Considerations

Continuous data will be described using descriptive statistics as follows: number of observations (n), mean, median, standard deviation, minimum, and maximum. All minimum and maximum values will be displayed with the same number of decimal places relative to the raw data, the mean and median will be displayed with one additional decimal place, and the standard deviation will be displayed with two additional decimal places.

Data listings will be displayed by subject identification number. Summary tables will be displayed by treatment arm for all subjects. For those summary tables in which baseline and change from baseline measurements will be presented, if time is not available the last observed measurement on or before the date of initial dose of study product will be considered the baseline measurement. If date and time are available the last observed measurement on or before the date and time of initial dose of study product will be considered the baseline measurement.

Study Day 1 is defined as the date of first dose of study product. For visits (or events) that occur on or after the first dose of study product, study day is defined as visit date (event date) – date of first dose of study product + 1. For visits (or events) that occur before the first dose of study product, study day is defined as visit date (event date) – date of first dose of study product. There is no Study Day 0.

For listings that include the derivation of “days since last dose,” this is defined as event date – date of last dose. Events that occur on the same day as the last dose of study product will therefore be described as occurring zero days from the last dose of study product.

When categorical data are presented, the percentage will be suppressed when the count is zero in order to draw attention to the non-zero counts. The denominator for all percentages, unless otherwise specified, will be the number of subjects in each treatment arm or overall.

Only nominal/scheduled visit data will be reported in the tables. All visits, including unscheduled visits, will be presented in the listings. Note that all scheduled visits should occur within ± 3 days of the protocol-specified visit schedule.

4.1. Sample Size

4.1.1. Arm P Reference Data

The Arm P reference data for planning this trial is specified as a median survival of 22 months based on the placebo arm of Dendreon D9902B. Using exponential assumptions the corresponding hazard rate is 0.3781 and the corresponding three-year survival is 32.2%.

4.1.2. Delay of Vaccine Effect

There is evidence, both from the PROSTVAC phase 2 study and other prostate cancer trials, as well as trials of therapeutic vaccines in other cancers, that there exists the possibility of a delay in the effect of the experimental vaccine. Taking into account the possibility of a delay in effect precludes using trial size computation methods that assume proportional hazards because the proportional hazards assumption is not valid if there is delayed effect. The existence of a delayed effect means that early deaths will not differentiate between the arms and therefore the number of deaths required for the same power will be greater. Thus, the use of methods that do not take into account delay of effect could lead to underestimating the power of the trial. Simulations were used for both delayed effect scenarios and scenarios where delayed effect was not assumed. [Appendix A](#) to this document describes the simulation methodology.

4.1.3. Effect Size for Survival

The hazard ratio in the specific alternative hypotheses used to compute trial size is 0.68, that is, a 32% smaller hazard rate in Arm VG or Arm V as compared to Arm P. This hazard ratio is based on hazard ratio estimates from the previously completed randomized phase 2 trial with an allowance that the phase 2 trial likely provides an over-optimistic estimate of the true hazard ratio. The hazard ratio estimate from the phase 2 trial was 0.56 when delayed effect is not taken into account, and was approximately 0.5 when delayed effect is taken into account (depending on the quantification of the delayed effect – see next paragraph).

Proportional hazards regression with time-dependent covariate implementation of delayed effect was used to obtain estimates of the ultimate hazard ratio following delayed effect in the previously completed randomized phase 2 study. It was found that estimates of this ultimate hazard ratio were reasonably uniform over a range of delayed effect specifications and that having delayed effect in the model resulted in a better fit to the survival data than models without delayed effect. The delayed effect estimate of the hazard ratio is approximately 0.5. The shape of the delay of effect used to plan this trial is based on that observed in the phase 2 study, but with an allowance that the phase 2 trial likely provides an over-optimistic estimate of the true hazard ratio.

The delay of effect used in the simulations done to plan this trial is based on that observed in the randomized phase 2 study. This delay of effect is characterized as follows: the hazard ratio is initially unity (no effect) for four months, and over the next four months transitions linearly to the hypothesized 0.68.

4.1.4. Power and Significance Level

The trial is planned so that a between-arm logrank test for all subjects will have the target power. The target power taking into account the possibility of a delay in effect is specified to be 85% or greater. The two comparisons will be done with Bonferroni correction to the overall type I error probability so that the type I error probability for each will not exceed one-sided 0.0125 ($=0.025/2$).

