The significance levels to be used for the analyses associated with these two comparisons will protect the overall study type I error probability to be one-sided 0.025 or less. The possibility of delayed vaccine effect is taken into account in computing the required number of deaths, (as modeled from the randomized Phase 2 trial). The projected trial size is 400 subjects per arm (approximately 1,200 subjects) with at least 85% power, and the final analyses will be event-driven and take place when 534 deaths have been realized for the comparisons involving all subjects randomized (Arm V+G versus Arm P, and separately Arm V versus Arm P).

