9.4 Primary Efficacy Analysis

Two main overall comparisons of survival time are planned: A comparison between Arm V+G and Arm P, and a comparison between Arm V and Arm P. Thus two separate tests will be assessed, and success for the trial is defined as meeting statistical criterion for either of the following comparisons.

- Superiority of Arm V+G over Arm P for all subjects randomized to these arms.
- Superiority of Arm V over Arm P for all subjects randomized to these arms.

The overall type one error probability (alpha error) for the whole study is designed as a one sided $P=0.025$. There are two main overall comparisons, which therefore necessitate a type one error probability to 0.0125 for each comparison based on using a Bonferroni correction.

The primary analysis methodology will be the stratified log rank test.

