8.2. Primary Analyses (Survival)

The survival outcome from subjects in each experimental arm, Arm V and Arm VG, will be compared separately to the survival outcome from subjects in the control arm, Arm P. If either of these comparisons passes the statistical criterion specified previously, then the trial will be regarded as having met the statistical criterion for success. This section defines the statistical method and criterion for each of these survival analyses.

The survival analysis objective is to ascertain whether the survival time distribution for subjects randomized to the experimental arm is consistent with longer survival as compared to subjects randomized to the control arm. All randomized subjects will be included in the primary survival analysis according to the randomized arm (intent-to-treat).

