8.2.2. Survival Analysis Method

Imputation of missing date parts will follow the rules previously specified. Competing events for death are “definite” lost to follow-up and withdrawal of consent for continued vital status assessments. Both of these competing events are subject to revision for an individual subject with the passage of time.

The primary analyses will be performed on the ITT set and will analyze subjects according to the randomized arm. The primary analysis will be repeated on the FAS as a sensitivity analysis.

The primary test of each endpoint will consist of a stratified logrank test for the test of the null hypothesis (STRATA <stratification-variable> / TEST=LOGRANK;). See [Section 4.2](#) for the definition of the stratification variable. The significance of the logrank test will be assessed by referring the one-sided stratified logrank test P_1 to 0.0125, and the comparison will be said to meet statistical criterion if $P_1 < 0.0125$.

Notes:

- These analyses must be stratified: Anderson et al. 2006.
- When there are competing events then censoring competing events provides a between-arm test of the event of interest: Prentice et al. 1978.

The hazard ratio for each comparison will be estimated using stratified (STRATA <stratification-variable>;) proportional hazard regression with the specification of ties handled by the exact method (TIES=EXACT option on MODEL statement). Two-sided 95% confidence interval will be reported in order to maintain consistency with the reporting of estimates from other prostate cancer studies.

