8.3. Secondary Endpoint (Alive Without Event [AWE] at Six Months)

The testing of AWE will have meaning in the context of type I error probability control only if the corresponding primary survival comparison meets its formal statistical criterion. The formal significance levels used for survival analysis will be used for AWE.

AWE has less statistical sensitivity than an analysis based on the closely related and traditional time-to-progression because the timing of events is ignored. Thus, AWE is inherently conservative. This trade-off is acceptable because the trial size provides adequate sensitivity for meaningful differences in the AWE proportions for each comparison. The approximate statistical sensitivity of AWE can be illustrated by assuming a simple comparison of proportions between the arms being compared. Assume a significance level of one-sided 0.0125 and that the control arm proportion is 0.5. Each comparison is based on 800 subjects, 400 per arm. The probability is 90% or greater that this statistical test will be significant if the true proportion difference is 0.126 or greater and the critical difference is 0.080.

The 95% confidence interval on the odds ratio estimate will be computed as the measure of the magnitude of effect.

All analyses of AWE will be conducted on the ITT set and repeated for the FAS as a sensitivity analysis.

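### Plain Bonferroni across the two vaccine arms leaves a winning arm's 0.0125 unused; a graphical procedure could pass it to the other arm's survival test within the same 0.025 limit

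*SAP*

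**What the plan says.** The protocol synopsis promises significance levels that "will protect the overall study type I error probability to be one-sided 0.025 or less". Protocol 9.4 implements this as "a type one error probability to 0.0125 for each comparison based on using a Bonferroni correction". SAP 4.1.4 agrees: "The two comparisons will be done with Bonferroni correction to the overall type I error probability". Its cap for either test is half of 0.025. SAP 8.2.2 judges each stratified logrank test against a fixed 0.0125. Success needs only one arm: "If either of these comparisons passes the statistical criterion specified previously" (SAP 8.2), the trial has met its criterion.

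Alpha is reused within an arm. Under SAP 8.3, an AWE result counts towards error control "only if the corresponding primary survival comparison meets its formal statistical criterion". On the level to apply, that section reads: "The formal significance levels used for survival analysis will be used for AWE". Protocol 9.6 likewise applies the survival levels to AWE.

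The structure is therefore two parallel branches of 0.0125, each running survival then AWE. Neither document lets a win in one arm raise the level for the other.

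**The concern.** The trial asks two questions: does PROSTVAC work with GM-CSF, and does it work without? Protocol 1.2.11 gives doubts about GM-CSF as the reason for the third arm, so the second regimen's result is not incidental. Once one arm has succeeded on everything in its branch, its 0.0125 has no further use, yet the other arm is still held to 0.0125. A closed testing procedure would allow up to 0.025 at that point. A regimen whose survival p-value falls between the two thresholds could not be claimed, although the trial-wide error limit would have permitted the claim.

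**Working it through.** **Inputs.** HR 1 for 4 months, then a linear ramp over 4 months to 0.68 (SAP 4.1.3); control median 22 months, 400 per arm, 534 deaths per comparison (SAP 4.1.5); 30-month accrual with a 19-month ramp (SAP Appendix B); efficacy levels 0.000135, 0.00147, 0.00501 and 0.01063 (SAP 12). The correlation ρ between the two survival statistics is not in the documents. It is 0.5 in theory with a shared control and about 0.39 in simulation under the delayed alternative; both are shown.

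**Reproducing the plan.** A three-arm simulation (10,000 trials, unstratified logrank, no loss to follow-up, no futility stopping) gave power of 85.5% and 85.8% per comparison at the final analysis, against 86.1% in SAP Table 1, Case 3. With the interim looks it gave 84.3% and 84.4%, against 83.88% in SAP 12. The O'Brien-Fleming levels for 0.0125 reproduce exactly.

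**Both arms winning, alpha passed directly between survival tests.** Let m = z(0.9875) + z(power), with critical values 2.241 (0.0125) and 1.960 (0.025), and let Φ2 be the bivariate normal distribution function.

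- Now: P(both) = Φ2(m − 2.241, m − 2.241; ρ).
- With recycling: P(both) = 2Φ2(m − 2.241, m − 1.960; ρ) − Φ2(m − 2.241, m − 2.241; ρ).

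| Power per arm | ρ | Now | With recycling | Gain (points) |
|---|---|---|---|---|
| 83.88% | 0.39 | 73.2% | 81.8% | 8.6 |
| 83.88% | 0.5 | 74.2% | 82.3% | 8.2 |
| 86.1% | 0.39 | 76.5% | 84.4% | 7.9 |
| 86.1% | 0.5 | 77.4% | 84.9% | 7.5 |

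The simulation with interims, judging the second arm on O'Brien-Fleming levels for 0.025 (0.00063, 0.0042, 0.0113, 0.0207), gave 73.9% rising to 81.7%, a gain of 7.8 points. Without delay the gain is 1.1 to 1.5 points. At weaker equal effects it reaches 10.9 points (ρ 0.5, about 62% power per arm). P(at least one win) stays at about 95%, because recycling starts only after a win.

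**Gain if alpha passes only after the winning arm's AWE also succeeds.** If AWE is independent of survival, the gain is the direct gain times AWE power. With the SAP 8.3 illustration (control 0.5, 400 per arm, level 0.0125), the null standard error is √(2 × 0.25/400) = 0.0354 and the critical difference is 2.241 × 0.0354 = 0.079, against 0.080 stated. Multiplying by 7.8 to 8.2 points:

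| Assumed AWE difference | AWE power | Gain (points) |
|---|---|---|
| 0 | 1.25% | 0.1 |
| 0.05 | 20% | 1.6 to 1.7 |
| 0.08 | 51% | 4.0 to 4.2 |
| 0.126 | 91% | 7.1 to 7.5 |

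Protocol 9.6 gives a stricter critical difference of 0.092, which would lower the last three rows.

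**Error control of the AWE-first order.** Take each AWE hypothesis as tested once.

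- Both survival nulls true: the first false rejection must occur at 0.0125 in one of two tests, so at most 0.025.
- One arm works on survival; its AWE and the other arm's survival are null: the two null tests are at 0.0125 each, and alpha moves across only after a false AWE rejection has already been counted. At most 0.025.
- One arm works on survival and AWE; the other arm's survival is null: one test at 0.025.
- Both arms work on survival, both AWE nulls true: 0.0125 each, at most 0.025.
- Only one AWE null true: at most 0.025.

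The cost appears when one arm is null. In the direct version, simulated false rejection of that arm rose from 1.2% to between 2.2% and 2.4%. The AWE-first version lies between the current rate and that.

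**The case against.** The strongest reply is that nothing here is broken. Success is defined as either arm, power is specified per comparison, and neither document sets a target for winning both. The two branches add up to 0.025 as promised. All of this stands: the gain is on a quantity the plan does not undertake to deliver.

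A second reply is that the 8 points and the absence of cost belong to different procedures. This also stands. The direct route defers the only secondary endpoint. The AWE-first route costs no current rejection, but may gain little: AWE is read at six months, while the planned survival effect is absent for four months and complete only at eight, and protocol 5.4.2 expects radiological progression during treatment.

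A third reply is that recycling would inflate error. That is true of one combination only. If a survival win funded both the other arm's survival test at 0.025 and its own AWE test at 0.0125, the bound would be 0.025 + 0.0125 = 0.0375 (1 − 0.975 × 0.9875 = 0.0372 under independence). Neither route described here does that.

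Finally, the interims carry futility rules, and SAP 12 leaves the action to DMC discretion when only one comparison crosses. The calculations include neither, so an amendment must say how the raised boundary fits with them.

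**Conclusion.** This is lost efficiency in a valid plan, not an error. A reader might infer that the plan discards all alpha after a win, that error control requires 0.025 for the second arm, or that the chance of trial success suffers. The documents support none of these: alpha already passes from survival to AWE within each arm, 0.025 is a permitted level and not a required one, and P(at least one win) does not change.

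At the planning alternative in both arms, the AWE-first order adds about 0.1 to 7.5 points to the chance of two survival wins. The range rests on assumed AWE differences of 0 to 0.126, control AWE of 0.5, and independence of AWE and survival. Direct passing adds about 8 points at that alternative. Eight is not a ceiling: the figure is about 1 without delay and about 11 at weaker equal effects. If one arm is null there is no benefit, and its own false-rejection rate can move from about 1.2% towards, but not above, 2.5%.

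**What to change.** In SAP 4.1.4, 8.2 and 8.3 and protocol 9.4, before any unblinded result is known to the sponsor, specify a graphical procedure for all four hypotheses:

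1. Test survival at 0.0125 in each arm, then that arm's AWE at 0.0125.
2. If both are rejected in one arm, pass its 0.0125 to the other arm's survival test. From that point on, judge that test on O'Brien-Fleming levels for 0.025 (about 0.00063, 0.0042, 0.0113, 0.0207).
3. If that survival test is rejected, carry the same alpha to that arm's AWE.

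State when AWE is tested, and how the raised boundary works with the futility rule and with DMC discretion when only one comparison crosses.

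The cost is amendment wording, with no extra subjects or deaths. Passing alpha directly from survival to survival is an option for the sponsor to weigh; it gives the full gain but defers formal AWE testing until both survival comparisons pass.

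In the same edit, reconcile the final criterion of 0.0125 in SAP 8.2.2 with 0.01063 in SAP 12. Using 0.0125 at the final analysis after the three interims would give about 0.0141 per comparison.

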4.1.5. Number of Subjects and Required Number of Deaths

The number of subjects per arm is set to be 400 (Approximately 1200 total subjects). The accrual rate distribution is 19 months of linear ramp up followed by 11 months of constant rate of accrual (2.5 years to accrue approximately 1200 subjects). Note: The accrual distribution assumptions have been updated from the assumptions used originally to plan this trial and are based on current accrual experience. The table below has been revised to reflect these new accrual assumptions and there is no material modification to power, hypothesized hazard ratio, or any other important aspect of the trial design. As expected, the revised computations do change the projections for time to analysis. The assumptions used in [Table 1](#) match the assumptions used in the interim analysis planning computations outlined on pages 23 and 24. Please see [Appendix B](#) for more detail around the 19 month linear ramp followed by 11 months constant rate of accrual.

The trial is planned as an event driven trial. Simulation is used to compute the required number of deaths after setting other specifications. [Appendix A](#) to this document describes the simulation methodology. [Table 1](#) below shows the results of the simulations.

Table 1: Simulation Results

Case #	Delayed Effect	Specified # deaths	Time to specified deaths (y)	1-sided type I error probability estimate (%)	Power estimate (%)	Critical hazard ratio
1	No	340	3.4	1.17	90.2	0.784
2	Yes	340	3.3	1.13	44.5	0.784
3	Yes	534	5.1	1.23	86.1	0.823
4	No	534	5.2	1.12	98.8	0.823

Notes:

- Simulations are for the comparison of one of the experimental arms to control arm, that is, 800 subjects, 400 per arm, accrued over two years, with a 19 month ramp time followed by a constant accrual rate for 11 months (2.5 year total accrual).
- 10,000 replications for each case.
- Significance level is one-sided 0.0125. The column “One-sided type I error probability estimate (%)” from the simulations should be approximately 1.25%. Target power with delayed effect is 85% or more.
- The control arm data are generated under the exponential distribution with 22 month median survival.
- The experimental arm data under the specific alternative and when delayed effect (if applicable) are generated so that hazard rates are equal for 4 months (hazard ratio = 1), followed by a linear transition over next 4 months to target hazard ratio of 0.68, with hazard ratio = 0.68 from 8 months onward.
- The estimated type I error and power are the percent rejection of the null hypothesis when the data are simulated under the null or specific alternative hypotheses, respectively. The estimated type I error probabilities in the table are sufficiently close to 1.25% considering they are estimated from simulations.
- The “Critical hazard ratio” is the maximum hazard ratio that resulted in rejection of the null. This is an estimate of the threshold of significance. At the end of the trial larger hazard ratios will not result in rejection of the null hypothesis.

Case # 1 simulates a trial without delayed effect and a target power of 90% or greater and corresponds to conventional (proportional hazards) trial sizing computations, where the usual formula computed a requirement for 340 deaths. Case # 2 is based on the required number of deaths computed for Case # 1 (340) but with the data in the simulations generated under the specified delayed effect. The power for an analysis at 340 deaths when the specified delayed effect is applicable is not sufficient (44.5%). Note that 340 deaths are realized sooner than for Case # 2 than Case # 1 because the experimental arm will have a higher early hazard rate in Case # 2 than in Case # 1.

Case # 3 represents a solution to the required number of deaths for a target power of 85% or more under the delayed effect specified. The number of deaths required is found to be 534, with time to realization of 534 deaths projected to be 5.1 years. Case # 4 illustrates the estimated power of a trial with 534 deaths at the final analysis but without delayed effect. The high power (98.8) is the result of early events being differentiating.

Thus, these simulations show that a final analysis at 534 deaths provides protection against unacceptable loss of power if the projected delayed effect is applicable, and yet assures that the type I error probability is protected. The trial's power will be 85% or greater if the delayed effect does not exceed that specified in the simulations.

